10.1.4 FUTURE USE OF DATA

Data collected for this study will be analyzed and stored at the Sponsor's headquarters. After the study is completed, the de-identified, archived data will be retained by the Sponsor and will not be used by other researchers outside of the study. Deidentified images obtained in the course of study conduct, will also be stored with other study data. All stored data may be used as part of future post-hoc analyses by the Sponsor.

10.1.5 SAFETY OVERSIGHT

Safety oversight will be under the direction of the Medical Monitor. The Medical Monitor will review SAEs related to the study and provide guidance on actions, if any, which need to be taken by the study team.

10.1.6 CLINICAL MONITORING

Monitoring of the clinical data collected for a study is performed to ensure that the rights and well-being of trial subjects are protected, that the reported trial data are accurate, complete, and verifiable, and that the conduct of the trial is in compliance with the currently approved protocol/amendment(s), with ICH GCP, and with applicable regulatory requirement(s).

- Monitoring for this study will be performed by the Sponsor or authorized Sponsor representative.
- Monitoring will incorporate risk-based (e.g., centralized) and on-site review of data. The frequency of monitoring visits will vary based on factors such as information seen during risk-based monitoring activities, frequency of enrollment, and other pertinent constraints (i.e., audit preparation, etc.). The extent of the monitoring will be to achieve comprehensive, 100% source data verification.
- The schedule of monitoring activities (i.e., timing of confirmation letters, reports, follow up letters, etc.) will follow the Sponsor's SOPs and the Clinical Monitoring Plan (CMP).

10.1.7 QUALITY ASSURANCE AND QUALITY CONTROL

Following written Standard Operating Procedures (SOPs), the monitors will verify that the clinical trial is conducted and data are generated and biological specimens are collected, documented (recorded), and reported in compliance with the protocol, ICH GCP, and applicable regulatory requirements (e.g., Good Laboratory Practices (GLP), Good Manufacturing Practices (GMP)).

The investigational site will provide direct access to all trial related sites, source data/documents, and reports for the purpose of monitoring and auditing by the sponsor, and inspection by local and regulatory authorities.

10.1.8 DATA HANDLING AND RECORD KEEPING

10.1.8.1 DATA COLLECTION AND MANAGEMENT RESPONSIBILITIES

Data collection is the responsibility of the clinical trial staff at the site under the supervision of the site Investigator. The Investigator is responsible for ensuring the accuracy, completeness, legibility, and timeliness of the data reported.

All source documents should be completed in a neat, legible manner to ensure accurate interpretation of data.

Hardcopies of the study visit worksheets may be provided for use as source document worksheets for recording data for each subject enrolled in the study. Data recorded in the eCRF derived from any source documents should be consistent with the data recorded on those source documents.

Clinical data (including AEs), concomitant medications, and expected adverse reactions data, and randomization) and clinical laboratory data will be entered into Clindex® (Fortress Medical Systems, Inc.), a 21 CFR Part 11-compliant data capture system provided by the Sponsor. The data system includes password protection and internal quality checks, such as automatic range

checks, to identify data that appear inconsistent, incomplete, or inaccurate. Clinical data will be entered directly from the source documents.

A randomization code will be developed by the Sponsor's Statistical and Data Management teams and will be entered into the EDC mentioned above. Only these teams will know or have access to these codes and/or the software systems used by the study's investigators. Randomization via the EDC system will only occur on Day 0 of the study after a subject meets all of the inclusion and exclusion criteria set forth in this protocol.

10.1.8.2 STUDY RECORDS RETENTION

Study documents should be retained until at least 2 years after the formal closure of the clinical trial at the study site. These documents should be retained for a longer period, however, if required by local regulations. No records will be destroyed without the written consent of the sponsor, if applicable. It is the responsibility of the Sponsor to inform the investigator when these documents no longer need to be retained. If the documents are to be moved from the original Investigator's site (i.e., for storage purposes), a formal letter must be sent to the Sponsor informing them of the move date, the new location, and, if there is a change in oversight of the documents, the person who will be retaining oversight. Letters can be sent to the Director of Global Clinical Operations at Integra LifeSciences. The Sponsor should be contacted for the current and appropriate address.

10.1.9 PROTOCOL DEVIATIONS

A protocol deviation is any noncompliance with the clinical trial protocol, ICH GCP, or any supplementary protocols provided by third party vendors which have bearing on the collection of clinical trial data.

Major protocol deviations are a subset of protocol deviations that might significantly affect the completeness, accuracy, and/or reliability of the study data or that might significantly affect a subject's rights, safety, or well-being.

The noncompliance may be either on the part of the subject, the Investigator, or the study site staff. As a result of major deviations, corrective actions are to be developed by the site and implemented promptly.

These practices are consistent with ICH GCP:

- [4.5 Compliance with Protocol](#), sections 4.5.1, 4.5.2, and 4.5.3
- [5.1 Quality Assurance and Quality Control](#), section 5.1.1
- [5.20 Noncompliance](#), sections 5.20.1, and 5.20.2.

It is the responsibility of the site Investigator to use continuous vigilance to identify and report deviations within 10 working days of identification of the protocol deviation, or within 5 working days of the scheduled protocol-required activity. All deviations must be addressed in study source documents, reported to the Sponsor. Protocol deviations must be sent to the reviewing IRB per their policies. The site Investigator is responsible for knowing and adhering to the reviewing IRB requirements. Protocol deviations and their impact on the data analysis will be addressed in the study's statistical analysis plan

10.1.10 PUBLICATION AND DATA SHARING POLICY

The results of the study may be published in scientific literature and may also be used in submissions to regulatory authorities. It is the intent of the Sponsor to publish or present the study results together with study results from the other sites, unless specific written permission is obtained in advance from the Sponsor to publish separate results. The Investigator will ensure that any site and/or Sponsor personnel making a significant contribution to the study or development of a manuscript are recognized as co-authors in any publication according to guidelines set forth by the International Committee of Medical Journal Editors (ICJME).

All information received by the Investigator concerning the Sponsor's business operations (such as patent applications, product design, formulae, manufacturing processes, basic scientific data, or characterization or formulation information supplied to the Investigator and not previously published) is considered confidential by the Sponsor and shall remain the sole property of the Sponsor. The Investigator agrees not to use it for any purpose other than conduct of the study without the prior written consent of Sponsor.

It is understood by the Investigator that the Sponsor will use the information developed in this clinical trial ("Study Data") in connection with the development of the AMNIOEXCEL Plus Placental Membrane. Therefore, Study Data may be disclosed to other Investigators or appropriate regulatory authorities. By agreeing to participate in this clinical trial, the Investigator understands that he/she has an obligation to provide the Sponsor with complete and accurate Study Data.

Publication and Disclosure: Because this is a multi-center trial, Investigators and/or their academic Institutions shall not independently publish, publicly disclose, present or discuss any Study Data or other information pertaining to their respective activities conducted under this study protocol until a multi-center publication is released under Sponsor's direction, unless otherwise agreed upon in the study agreement.

10.1.11 CONFLICT OF INTEREST POLICY

The independence of this study from any actual or perceived influence is critical. Therefore, any actual conflict of interest of persons who have a role in the design, conduct, analysis, publication, or any aspect of this trial should be disclosed and managed. Furthermore, persons who have a perceived conflict of interest should have such conflicts managed in a way that is appropriate to their participation in the design and conduct of this trial.

10.1.12 FINANCING AND INSURANCE

This study is being financed by the Sponsor, Integra LifeSciences, Inc. The Sponsor holds a certificate of insurance for this study.

10.2 ABBREVIATIONS AND DEFINITIONS

Table 4: Abbreviations/Definitions

Abbreviation/Term	Clarification/Definition
ABI	Ankle-Brachial Index
AE	Adverse Event
AMNIOEXCEL Plus	AMNIOEXCEL® Plus Placental Allograft Membrane; the investigational product
Apligraf	a living, bi-layered skin substitute; the comparator investigational product
AR	Adverse Reaction
CFR	Code of Federal Regulations
CMH	Cochran–Mantel–Haenszel
CMP	Clinical Monitoring Plan
CONSORT	Consolidated Standards of Reporting Trials
DAMA	Dehydrated Amniotic Membrane Allograft
DFU(s)	Diabetic foot ulcer(s)
dHACM	dehydrated Human Amnion/Chorion Membrane
eCRF	Electronic Case Report Forms
EDC	Electronic Data Capture
FDA	Food and Drug Administration
GCP	Good Clinical Practice
HbA1c	Glycosylated Hemoglobin (A.K.A., Hemoglobin A1C)
HCT/P	Human Cellular and Tissue Based Products
HIPAA	Health Insurance Portability and Accountability Act
ICH	International Conference on Harmonisation
ICMJE	International Committee of Medical Journal Editors
IRB	Institutional Review Board
ITT	Intention-To-Treat
LOCF	Last Observation Carried Forward
LTFU	Lost-to-Follow-Up
PP	Per-Protocol
SAE	Serious Adverse Event
SAP	Statistical Analysis Plan
SOC	Standard of Care
SOP	Standard Operating Procedure
T-AEPDFU-001	Protocol Number
T-PAM	Tri-layer Placental (Amnion/Chorion/Amnion) Allograft Membrane (T-PAM)
TcPO ₂	Transcutaneous Oxygen Level
US	United States

[Intentionally Blank]

10.3 PROTOCOL AMENDMENT HISTORY

Table 5: Protocol Amendment History

Version	Date	Description of Changes	Brief Rationale
1.0	14 Feb 2018	N/A, Original Version	N/A, Original Version
2.0	01 Aug 2018	
 1. Removing Medical Monitor Information 2. Table 2 and Sections 8.1.4 and 8.2 were modified to allow for no imaging in the Apligraf cohort at Week 1. 3. Added numbering to sections in 6.1.2. 	
 1. Change in staffing; if sites require medical assistance, they will be provided with current appropriate staff member’s information. 2. Per the manufacturer’s instructions, the non-adherent layer should not be removed to allow for full integration of the product into the surface of the wound. See Section 6.1.2 Utilization and Administration, point 5 of the Apligraf Instructions for Use. 3. To assist with and clarify edits above.
3.0	05 Nov 2018	
 1. Modified language in Study Design the Summary section 2. Added the following language to section 7.2: “If the subject’s wound is open at follow-up week 1, the subject will be exited. They will be noted as having completed their study requirements.” 3. The following language was added to section 8.1.6: “IMPORTANT: If the subject’s wound is open at Follow-up visit 1 (e.g., week 13), the subject is exited from the study and is marked as having completed their study requirements. The site will note why they believe the wound is still open.” 4. Figure 1 and Table 2 have been updated 	
 1. To clarify and be in line with the other changes in this document. 2. To clarify what should happen to subject’s whose wounds re-open at follow-up visit 1. 3. To clarify what should happen to subject’s whose wounds re-open at follow-up visit 1. 4. These changes were made to be in line with the changes previously mentioned.

This document provides a detailed description of the statistical methods and procedures to be implemented during the analysis of the clinical study. The methods and procedures are intended to support the generation of study report, including detailed descriptions of the populations and methodologies, as well as summary tables, listings and graphics.

This statistical analysis plan (SAP) is based on Version 3.0 of the Protocol# T-AEPDFU-001.

2. Study Objectives

2.1. Primary Efficacy Endpoint

The primary objective of this study is to compare outcomes associated with the use of AMNIOEXCEL Plus Placental Allograft Membrane, Apligraf living, bi-layered skin substitute and SOC in the management of DFUs.

2.2. Secondary Efficacy Endpoints

The secondary endpoints include:

- Determine the proportion of subjects in each study arm with complete closure of the study ulcer at or before 12 weeks of treatment.
- Determine the time to complete wound closure in each study arm.
- Determine the rate of wound closure in each study arm.
- Assess medical resource utilization outcomes in each study arm.

2.3. Exploratory Endpoints

- The proportion of subjects in each cohort whose wounds are closed at 4 weeks of treatment.
- The effect of any covariate on the primary endpoint.

2.4. Safety Endpoints

The safety objective of this study is to assess adverse events associated with either of the study treatments and/or all study procedures in the management of DFUs.

Confidential Page 7 of 23

3. Study Design

3.1. Overall Design

This is a prospective, multicenter, parallel-group, randomized, three-arm trial designed to assess the proportion of ulcers achieving complete wound closure and confirmed 2 weeks later in a population with adequate arterial circulation, following up to 11 weeks of either AMNIOEXCEL Plus Placental Allograft Membrane with SOC, Apligraf bi-layered skin substitute with SOC, or SOC alone.

Subjects will be randomized 1:1:1 to receive one of the following:

- AMNIOEXCEL Plus Placental Allograft Membrane with SOC
- Apligraf bi-layered skin substitute with SOC
- SOC alone

3.2. Scientific Rationale for Study Design

Prospective, multicenter, randomized studies provide the most objective methods for analyzing the outcomes of multiple treatment groups. The use of a three-cohort study allows simultaneous comparison of the treatment in question utilizing an active comparator and current SOC, the true baseline.

3.3. Justification for Investigational Products/Treatments

While there may be generalizable evidence that all tissue-based allografts outperform SOC therapies in the management of DFUs, the performance of specific products varies. Although there is evidence that AMNIOEXCEL Amniotic Allograft Membrane outperforms SOC procedures, AMNIOEXCEL Plus Placental Allograft Membrane has not been assessed as an advanced wound therapy for DFUs.

The comparator treatment, Apligraf, has been investigated as an advanced treatment for patients with DFUs and has been compared to SOC procedures.

The use of an offloading boot is a known and widely used SOC adjunctive therapy. Clinical studies have shown that offloading with rigid boots provide a more aggressive healing rate as compared to shoes, custom insoles, wheelchairs, bedrest, and/or crutches. The use of a boot in this clinical trial, in addition to moist wound dressings, will provide the most robust baseline to compare the active treatments (i.e., investigational products) against.

Confidential Page 8 of 23

3.4. End of Study Definition

The study is considered completed after all of the screened and enrolled (i.e., randomized) subjects have completed all of their study treatments and been signed off by the investigative sites in the electronic data capture (EDC) system.

[figure not shown]
4. Study Procedure

The flow chart and schedule for this study are as follows (sections 4.1 and 4.2). Additional information concerning the conduct of the study can be found in the referenced protocol.

Confidential Page 9 of 23

4.1. Study Flow Chart

Figure 1: Study Schema

Page 10 of 23

4.2. Schedule of Activities

| | | Screening | juj | | | | | | | Treatment | | | | | | | Follow-(| Follow-Up Visits | |
|--|-----------------------------------|------------|-----------|-------|----------|----------|-------------|-----------|--------|-----------|-----------|-------------|-----------|----------------------|-----------|----------|-----------|------------------|----------|
| Store 2. Weeks 1. Week 1. Week 2. Week 2. Week 2. Week 2. Week 3. We | Procedures | Visit 1 | Visit 2 | | | | | 1 | | | | | | | | | Vicir 1b | Vicit 3 | |
| 1423 Ax Ax Ax Ax Ax Ax Ax A | (See Section 8 for | -2 Weeks | -1 Week | | Week 1 | Week 2 | | Week 4 | Week 5 | Week 6 | Week 7 | | Week 9 | Week 10 ² | Week 11ª | Week 12ª | | | Unsched. |
| Higher X | | -14±3 days | .7±3 days | Day 0 | 7±3 days | 14±3 day | 8 | 28±3 days | | 42±3 days | 49±3 days | 56±3 days 6 | 33±3 days | 70±3 days | 77±3 days | | 01+3 days | 00+3 dans | Visit |
| 19 19 19 19 19 19 19 19 | Inf. Consent & HIPAA | × | | | | | | | | | | | | | | | | | |
| Second S | Eligibility Criteria | × | ×c | × | | | | | | | | | | | | | | | |
| Pition X | Demographics & Medical History | × | | | | | | | | | | | | | | | | | |
| Option O | Physical Examination | × | | | | | | | | | | | | | | | | | |
| pliance | Vascular Perfusion Assessment | × | | | | | | | | | | | | | | | | | |
| A | Treatment Compliance Review | × | × | × | × | × | × | × | × | × | × | × | × | × | × | × | | | × |
| ege | Debridement ^d | × | × | × | × | × | × | × | × | × | × | × | × | × | × | | | | × |
| eg | Photography | × | × | × | × | × | × | × | × | × | × | × | × | × | × | × | × | × | × |
| e b | Ulcer Assessments [‡] | × | × | × | × | × | × | × | × | × | × | × | × | × | × | × | × | × | × |
| Prod. X | Standard of Care [§] | × | × | | × | × | × | × | × | × | × | × | × | × | × | | | | |
| Prod.' or of the cedures o | Boot Application ^h | × | × | × | × | × | × | × | × | × | × | × | × | × | × | × | × | × | × |
| Prod.* or of the cedures o | Randomization | | | × | | | | | | | | | | | | | | | |
| In the last of t | Investigational Prod. | | | × | × | × | × | × | × | X | × | × | × | × | × | | | | × |
| cedures X </td MRU Assessment				×	| MRU Assessment | | | | × | × | × | × | × | × | × | × | × | × | × | × | × | × | × |
| x x x x x x x x x x x x x x x x x x x | ConMeds & Procedures | × | × | × | × | × | × | × | × | × | × | × | × | × | × | × | × | × | × |

Randomization will be used to minimize bias in this open label study. Randomization will occur in a 1:1:1 ratio and use a mixed block methodology. No blinding is possible. As well, no analytical blinding will occur during data review and/or analysis.

7. Interim Analysis

An interim analysis will occur after 50% of subjects have met the primary endpoint of the study. Descriptive statistics will be provided. Primary and secondary endpoints will be evaluated at the time of interim analysis. There is no hypothesis testing for the interim analysis, and thus no alpha allocation is considered.

8. Analysis Populations

8.1. Intent-to-Treatment Population

The Intent-to-Treat (ITT) population, defined as all randomized subjects who received at least one application of study intervention, will be the primary population for the analysis of primary and secondary efficacy endpoints.

Confidential Page 12 of 23

8.2. Per Protocol Population

The Per Protocol (PP) population, defined as all subjects in the ITT population for whom there were no major protocol violation, will be used as supportive for the analyses of the primary and secondary endpoints.

For the per protocol analysis, no data points will be imputed, all missing values will remain as missing.

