	
AMNIOEXCEL Plus Placental Allograft Membrane with SOC, Apligraf bi-layered skin substitute with SOC, or SOC alone.
 
Sample Size A total of 114 subjects, 38 per cohort, will be randomized, inclusive of a 20% in-study attrition rate.
 
It is assumed that the maximum wound closure rate is 90% with no difference between the study cohorts. Based on the 38 subject per cohort sample size, the half width of the 95% confidence interval for the wound closure rate is 13.5%. However, the study is not adequate for hypothesis testing.
 
Data Evaluation
 
The Intent-to-Treat (ITT) population, defined as all randomized subjects, will be the primary population for the analysis of primary and secondary efficacy endpoints.
 
Analysis Population
 
The Per Protocol (PP) population, defined as all subjects who complete the study without a major protocol violation, will be used as the primary analysis dataset.
 
Primary Efficacy Analysis
 
For the primary efficacy analysis, ITT population will be used. The proportion of subjects with complete wound closure, will be compared using the Cochran–Mantel–Haenszel (CMH) test. For the primary efficacy analysis, missing values will be imputed using last observation carried forward (LOCF). The differences in complete wound closure rates between treatment arms will be summarized and 95% confidence intervals calculated.
 
Safety Assessment
 
Adverse Events related to the investigational products, study ulcer and/or study procedures and all Serious Adverse Events will be recorded. All safety parameters will be summarized descriptively by treatment assignment. No inferential statistics are planned.
 
Exploratory Analyses
 
Exploratory analyses will be performed to examine wound closure status at Week 4 of Treatment and co-variate impact on the primary endpoint.

--	---

Figure 1: Study Schema

[figure not shown]

Table 2: Schedule of Activities

Procedures (See Section 8 for details)	Screening		Treatment													Follow-Up Visits		Unsched. Visit
	Visit 1 -2 Weeks -14±3 days	Visit 2 -1 Week -7±3 days	Random-ization Day 0	Week 1 7±3 days	Week 2 ^a 14±3 day	Week 3 ^a 21±3 days	Week 4 ^a 28±3 days	Week 5 ^a 35±3 days	Week 6 ^a 42±3 days	Week 7 ^a 49±3 days	Week 8 ^a 56±3 days	Week 9 ^a 63±3 days	Week 10 ^a 70±3 days	Week 11 ^a 77±3 days	Week 12 ^a 84±3 days	Visit 1 ^b Week 13 91±3 days	Visit 2 ^b Week 14 98±3 days	
Inf. Consent & HIPAA	X																	

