7 STUDY INTERVENTION DISCONTINUATION AND SUBJECT DISCONTINUATION/WITHDRAWAL

7.1 DISCONTINUATION OF STUDY INTERVENTION

For Subjects Who Develop an Infection:

Subjects who, during the course of the Treatment Phase, develop clinical signs and/or symptoms of infection (e.g., erythema, edema, pain, inflammation, increased drainage etc.) and in the opinion of the Investigator, require oral antibiotic therapy may receive a single course of oral antibiotics during the Treatment Phase of the study. **Should a second consecutive course be required/desired, the subject will be exited from the study.** This antibiotic therapy will be noted on the Concomitant Medications eCRF.

In addition to the above, for those subjects receiving Apligraf or AMNIOEXCEL Plus and develop signs/symptoms of infection, application of those allografts will be withheld on that visit. Application of allografts may be withheld for no more than 1 week at a time and no more than twice (non-consecutive visits) during the 12-week Treatment Phase. If signs and symptoms of infection requiring antibiotic therapy persist for more than one visit, or appear on more than 2 non-consecutive visits during the Treatment Phase, the subject will be discontinued from study participation.

For Subjects Whose Wound Closes:

Discontinuation from treatment in any of the study cohorts does not mean discontinuation from the study. There is one scenario in which a subject may continue in the study after intervention is final:

After treatment with AMNIOEXCEL Plus, Apligraf, and/or SOC **AND** if the subject's wound is documented as closed at or before week 12, the subject will continue to be monitored for two weeks to confirm wound closure. This is noted as week 13 and 14 in the Schedule of Activities, above, but may occur earlier.

If the subject's wound has NOT closed by week 12, the subject will be considered a study failure and will not have any further study visits.

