8.3. Safety Population

The Safety population is defined as all subjects receiving the allocated treatment after randomization. This population will be used for the analysis of safety endpoints.

9. Description of Efficacy Endpoints and Analyses

The primary analysis of the primary efficacy endpoint will be performed using the ITT population. The sensitivity analysis of the primary endpoint will be performed using the PP population. All secondary efficacy endpoints will be performed using the ITT population. Safety analysis will be based on the safety population.

In efficacy or exploratory analyses, covariate analyses will be conducted to assess the impact of various prognostic factors on closure and to demonstrate the robustness of the primary analysis. Prognostic factors (i.e., covariates) will be included if they are found to be contributing factors (i.e., the individual covariate p-value is less than 0.10). Potential prognostic factors to be considered include:

• Ulcer area

Duration of ulcer

Gender

• HbA1c

•Ulcer Location

Diabetes type

• Race

• Nicotine Use

Baseline BMI

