9.5. Missing Data

For primary efficacy evaluation of data points, the last available observation (LOCF) will be used. In the analyses of using the planimetry data, the last available planimetric value will be used for a discontinued subject. All subjects discontinued during the treatment period and before 100% wound closure during the treatment phase of the study will not be replaced and will be considered treatment failures for evaluating the primary and secondary endpoints.

10. Description of Other Variables and Analyses

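### SAP 8.2 and 9.5 conflict on subjects who exit with an open wound, and the literal 8.2 reading raises the per-protocol closure rate above the SAP's own failure rule

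*SAP*

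**What the plan says.** Four places bear on who counts in the PP analysis, and how.

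- **SAP 8.2, membership:** "defined as all subjects in the ITT population for whom there were no major protocol violation, will be used as supportive". Completion is not required. Protocol 9.3 has the same membership condition.
- **SAP 8.2, missing data:** "For the per protocol analysis, no data points will be imputed, all missing values will remain as missing".
- **SAP 9.5:** "All subjects discontinued during the treatment period and before 100% wound closure during the treatment phase of the study will not be replaced", and they are classed as treatment failures for the primary and secondary endpoints. No analysis population is named.
- **Protocol synopsis:** the PP set is "defined as all subjects who complete the study without a major protocol violation, will be used as the primary analysis dataset". This adds completion as a condition.

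The opening of SAP Section 9 gives the PP analysis its role: "The sensitivity analysis of the primary endpoint will be performed using the PP population".

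Protocol 7.1 and 7.2 provide for exits during treatment that need not involve any violation, such as an adverse event or a persistent infection, after which "the subject will be discontinued from study participation".

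SAP 9.1 (and Protocol 9.1) define a further group. A wound that closed by Week 12 but whose subject missed a follow-up visit is undetermined, and may enter unspecified extended analyses.

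**The concern.** Take a subject who exits for infection at Week 5 with an open wound and no major violation. Under SAP 8.2 this subject is in the PP set but has no Week 12 or confirmation reading. One rule leaves the outcome missing, so the subject drops out of the closure proportion. The other makes the subject a failure. The synopsis removes the subject from the set altogether. Two programmers working from the same SAP could report different PP closure rates, each with a text to cite.

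The choice has a direction. A subject discontinued before closure has an open wound by definition, so dropping such subjects raises the closure rate relative to the 9.5 rule. This is the only analysis the SAP labels a sensitivity analysis of the primary endpoint. If it changes the population and the missing-data rule together, a difference from the primary result cannot be traced to either. The study is open label, with no blinding at the analysis stage, so the rule should be settled in writing.

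**Working it through.** **Inputs from the documents.** 38 subjects per arm including 20% attrition, and a maximum closure rate of 90%, equal across arms (Protocol 9.2, SAP Section 5).

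**The plan's own figures.** 30/0.80 = 37.5, rounded up to 38, so the plan is consistent with about 30 completers and 8 exits per arm. The stated 13.5% half-width reproduces as the interval for a difference between two arms: 1.96 × √(2 × 0.9 × 0.1/38) = 13.5%. For a single closure rate, which is how the plan labels it, the same formula gives 1.96 × √(0.9 × 0.1/38) = 9.5%. The steps below do not use the half-width.

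**Assumptions.** All 8 exits are open wounds before closure. There are no major violators. The 90% is read as the rate among subjects with an outcome, because with 8 open-wound exits the failure-rule rate cannot exceed 30/38 = 78.9%. The 50% rate and all other exit counts are illustrative.

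**Formula.** Let n be the arm size, m the open-wound exits and r the closure rate among the n − m subjects with an outcome. Closures number r(n − m).

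- Exits left missing: PP rate = r(n − m)/(n − m) = r
- Exits counted as failures: rate = r(n − m)/n = r(1 − m/n)
- Gap = r × m/n

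**Results, n = 38, m = 8.**

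| r | Exits missing | Exits as failures | Gap (points) |
|---|---|---|---|
| 90% (plan) | 27/30 = 90.0% | 27/38 = 71.1% | 18.9 |
| 50% (assumed) | 15/30 = 50.0% | 15/38 = 39.5% | 10.5 |

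Over r from 30% to 90% and 4 to 12 exits, the gap runs from 0.30 × 4/38 = 3.2 points to 0.90 × 12/38 = 28.4 points.

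**Between arms.** Unequal exits can act either way.

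- Equal closures among all randomized, 19/38 in each arm, with 8 and 4 exits: leaving exits missing gives 19/30 = 63.3% and 19/34 = 55.9%, a 7.5-point difference that the failure rule does not show.
- Equal closure of 50% among those with an outcome, with 4 and 12 exits: leaving exits missing gives 17/34 = 13/26 = 50.0%, no difference. The failure rule gives 17/38 = 44.7% and 13/38 = 34.2%, a difference of 10.5 points. At r = 90% it is 0.90 × (12 − 4)/38 = 18.9 points.

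**Closed but unconfirmed wounds.** These are also missing when nothing is imputed. Suppose LOCF carries closed forward in the ITT analysis, with 8 of 38 missing and 15 of the other 30 confirmed closed (PP = 50.0%):

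| Open exits | Undetermined | ITT | PP minus ITT (points) |
|---|---|---|---|
| 8 | 0 | 15/38 = 39.5% | +10.5 |
| 4 | 4 | 19/38 = 50.0% | 0.0 |
| 2 | 6 | 21/38 = 55.3% | −5.3 |

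**The case against.** The strongest reply is that SAP 9.5 already covers PP. It names no population, and it can be read as classifying an outcome rather than imputing one. That fits SAP 9.1, where a wound still open at Week 12 is a failure. On this reading the 8.2 sentence merely switches off LOCF, and nothing is inflated. The reading is reasonable, but the SAP does not state it, and the wording of 8.2 covers all missing values without exception. What remains is an unresolved conflict, not a settled exclusion. The synopsis condition is a separate inconsistency that this reading does not remove.

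A reader might infer four stronger things that the documents do not support.

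- *That the PP rate can only rise.* This holds against the 9.5 failure rule for open-wound exits. It does not hold against ITT with LOCF, because subjects with closed but unconfirmed wounds leave the denominator too. Against the true 12-week rate, it would need exits to be less likely to close than those who stayed. That is plausible but not shown.
- *That the arm with most exits gains most.* The gap is r × m/n, so closure rates matter as well. Ten exits with 8/28 closed shifts 28.6% to 21.1% (7.5 points); six exits with 22/32 closed shifts 68.8% to 57.9% (10.9 points).
- *That the allograft arms must lose more subjects to infection.* The mandatory wording sits in the allograft paragraph of Protocol 7.1, but 7.2 lists similar grounds for all subjects, as something the investigator may act on. The second-antibiotic-course exit in 7.1 applies to everyone.
- *That PP would manufacture a treatment effect.* The 7.5-point example takes the failure rule as truth; the 4-versus-12 example shows the reverse.

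It is also fair that some exits, for significant non-compliance or a newly met exclusion criterion, may already be outside PP as major deviations, and that covariate analyses are planned as a further robustness check.

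**Conclusion.** The point holds as a conflict to be reconciled. Followed literally, SAP 8.2 or the synopsis removes open-wound exits without a major violation from the PP denominator, and the PP closure rate then exceeds the SAP's own failure-rule rate by r × m/n. At the planned arm size and attrition that is 18.9 points at 90% closure and 10.5 points at an assumed 50%, provided all attrition is open-wound exit among otherwise PP-eligible subjects. Fewer such exits shrink the gap in proportion.

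The consequence is confined to the supportive analysis. The SAP's primary analysis is ITT, and the plan itself says the study is not powered for hypothesis testing. The synopsis label of PP as the primary dataset conflicts with its own ITT statement and with the SAP, so it does not extend the effect to the primary result. The matter should be corrected, but it does not undermine the primary analysis.

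**What to change.** 1. In SAP 8.2, qualify the missing-data sentence: *PP subjects discontinued in the Treatment Phase before closure are closure failures, as in Section 9.5.*
2. In the same place, give one rule for undetermined closures in PP, identical to the rule in the primary analysis, and show the alternative alongside. Step 1 alone is not enough. With 15 confirmed closures, 15 confirmed failures, 4 open exits and 4 undetermined closures, PP would be 15/34 = 44.1% against 19/38 = 50.0% in ITT if LOCF carries closed forward.
3. In the synopsis, remove the completion condition from "defined as all subjects who complete the study without a major protocol violation", so that membership matches Protocol 9.3 and SAP 8.2.
4. State that discontinuation is not by itself a major protocol violation. Judge exits for non-compliance or eligibility under Protocol 10.1.9; do not declare every Protocol 7.2 exit violation-free.

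SAP Section 12 shows that the photograph-review data had already been evaluated, so date the change and give its reason.

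The cost is a few sentences and no new data. PP closure rates become less favourable than under the literal 8.2 reading.
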